3.1.1 Unscheduled visits

Subjects who attend at their own volition, (or as instructed to do so by the investigator) rather than for a scheduled study visit, will be examined and the visit will be classified as 'unscheduled'. Data collected at these visits will be recorded on the CRFs.

Should a subject attend for their initial visit and be ineligible for the study owing to a reason which the investigator believes to be transient (for instance slit lamp signs higher than those acceptable according to inclusion/exclusion criteria), a repeat first visit can be conducted a short time later. This visit may involve some or all of the scheduled initial visit procedures, with the exception of the consent process, which would not be repeated.

3.1.2 Missed visits

Subjects not attending for a visit will be contacted and encouraged to return for assessment. If two consecutive study visits are missed, the subject will be discontinued. It is expected that study site personnel will attempt all reasonable means of communication in this event, including corresponding with the subject by letter.

3.2 Visit conduct

3.2.1 Pre-enrolment

The subject will receive a study-specific information form outlining the study at least 24 hours before the initial visit.

3.2.2 Initial visit

Subjects should attend wearing their spectacles.

They will then be required to sign an informed consent form prior to enrolment [REDACTED]

[REDACTED] A copy of the signed form will be issued to the subject. When the subject has signed the consent form, they are considered to be enrolled on the study.

Subjects will be instructed on the following:

1. Lens handling, application and removal, where necessary.
2. Specific study instructions, such as the importance of not using any other contact lens products.
3. General contact lens information such as the management of red eyes.

2

3.

[figure not shown]
4. Slit lamp biomicroscopy will be carried out for the signs outlined in Table 4. Grades will be scored to the nearest 0.1 unit in the best judgement of the investigator using Efron Grading Scales:

- a. Using the recommended settings for slit width, magnification and filter, examine the anterior eye. Biomicroscopic signs listed in Table 4 should be graded.
- b. Instil sodium fluorescein (using a fluorescein ophthalmic strip wetted with saline) in both eyes and using cobalt blue light and a Wratten 12 filter or similar yellow filter, examine and grade the following: corneal and conjunctival staining.
- c. [REDACTED]

d. The upper eyelid should then be everted and examined both with cobalt blue light (with the yellow filter in place) and with white light (no filter in place). The grading of upper palpebral conjunctivitis should then be made with the Efron Grading Scales.

Classification	Primary signs	Secondary signs
Signs	Conjunctival redness Limbal redness Cornea neovascularisation Epithelial microcysts Cornea oedema Cornea staining Location of staining Conunctival staining Papillary conjunctivitis	Bephrats Meibomian gland dysfunction Mucin basis
Score	Efron Grading Scores (scored to nearest 0.1)	Efron Grading Scores (scored to nearest 0.1) (except mucin basis, where the numbers are recorded)

Table 4: Biomicroscopic signs. Staining assessed with sodium fluorescein.

13. Lens fit will be assessed using the following evaluations: horizontal and vertical centration, corneal coverage and movement. Normally, for an acceptable fit, centration and movement will fall within currently accepted clinical criteria [between -1 and +1 on a -2 to +2 grading scale] [REDACTED]
14. [REDACTED]
[REDACTED]
15. The first lens pair will be removed and discarded.
16. Using the fitting set, the second lens pair will be fitted according to the randomisation table [REDACTED] selecting the closest available lenses for the subject's prescription.
17. Procedures are repeated for the second lens pair, as outlined in steps 6 to 15 above.
18. The subject will be discharged, and the study lenses ordered. Subjects are allowed to wear their own lenses until the next visit.

Where possible, for a single subject, the same spherical and cylindrical BVPs should be ordered for the two lens types – the axis ordered may vary for the lenses due to the different stabilisation characteristics of the lenses. However, if the fitting process indicates that a different spherical and/or cylindrical BVP needs to be ordered, this will be permitted.

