1.4 Study outcome measures

The primary outcome measure for this study is subjective handling on lens removal. Secondary measures are lens fit parameters and biomicroscopy scores [REDACTED]

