1.6 Statistical considerations

The principal hypothesis to be tested in this work is that handling on lens removal scores for the two lenses are the same. Secondary hypotheses are that [REDACTED]

[REDACTED] lens fit parameters and biomicroscopy scores are also the same.

[REDACTED] such, these will

be compared using linear regression models or other parametric methods. Subjective preferences will be compared using chi-squared tests. Lens fit data are expected to be ordinal data and assessed with non-parametric approaches. Deviations from this statistical plan will be discussed in the final report. Deviations may be necessary due to differences between the actual data distribution compared with the anticipated data distribution.

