1.6.1 Power analysis

Power analysis using data from a previous study for subjective scores for lens removal on a 0-10 scale indicated that 50 subjects are required to complete the study to provide 90% power, assuming a standard deviation of 1.5 units for intra-subject differences and a meaningful difference of 0.7 units¹. To allow for discontinuations, up to 55 subjects will be enrolled.

¹ Based on the work of Papas et al. (2011).

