3.2.3 Dispensing 1 visit

Subjects should attend this visit wearing their spectacles. Subjects attending this visit wearing contact lenses should be rescheduled.

The following procedures will be performed (any ocular measurement procedures outlined below will be carried out on each eye):

1. [REDACTED]
[REDACTED]
2. Any medical or ocular issues since the last visit will be recorded.
3. [REDACTED]
4. The subject will apply the first randomised pair of lenses. Orientation of toric markings do not need to be taken into consideration.
5. Lenses are allowed to settle for five minutes.
6. Toric lens fit will be assessed as described in Section 3.2.2.
7. [REDACTED]
[REDACTED]
[REDACTED]
[REDACTED]
[REDACTED]
[REDACTED]
[REDACTED]
[REDACTED]
[REDACTED]
8. Lens fit will then be assessed using the following evaluations: horizontal and vertical centration, corneal coverage and movement, using the grading scales in
[REDACTED]
9. [REDACTED]
[REDACTED]
10. [REDACTED]
[REDACTED]
[REDACTED]
11. The investigator will confirm that lens fit [REDACTED] are satisfactory:
 - a. In the case of an unacceptable lens fit, proceed to the next randomised lens (on the same day, or as a separate visit).
 - b. In the case of unacceptable vision (less than 6/12), if in the opinion of the investigator an alternate lens from within the available power range would improve vision, then new lenses can be ordered and this visit repeated. If an alternate lens is not indicated then proceed to the next randomised lens (on the same day, or as a separate visit).
12. [REDACTED]
[REDACTED]

13. The subject will be issued with 10 pairs of contact lenses for the first study period.
14. The subject will then be discharged and asked to return for the one-week follow-up visit having worn the study lenses for at least two hours. Subjects should be asked to wear their lenses for a minimum of eight hours per day, five days per week.

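### Lens fit is graded -2 to +2 with good fit in the middle: does section 1.6 need to name the tested variable?

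*Combined protocol and SAP*

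**What the plan says.** Section 1.4 makes lens fit a secondary outcome: "Secondary measures are lens fit parameters and biomicroscopy scores". Section 3.2.2 (step 13) lists the components: "Lens fit will be assessed using the following evaluations: horizontal and vertical centration, corneal coverage and movement". For the centration and movement grades it adds that, in an acceptable fit, "centration and movement will fall within currently accepted clinical criteria [between -1 and +1 on a -2 to +2 grading scale". No such range is visible for corneal coverage.

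Section 1.6 gives the secondary hypothesis, that "lens fit parameters and biomicroscopy scores are also the same", and the method: "Lens fit data are expected to be ordinal data and assessed with non-parametric approaches". The visible text does not say whether the signed grade, its distance from 0 or acceptable/unacceptable status is compared. It names no test and does not say how the two eyes are combined. Text beside these sentences, and the references to the grading scales, are blacked out.

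At dispensing (section 3.2.3, step 11a) fit is checked before the lenses are issued: "In the case of an unacceptable lens fit, proceed to the next randomised lens".

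**The concern.** On this scale the sign records direction and the distance from 0 is the natural measure of quality. An analyst who reads that the data are ordinal, in a crossover, may well reach for a Wilcoxon signed-rank test on the recorded grade. If one lens is displaced more often than the other, equally in both directions, the positive and negative differences cancel. The report could then state that fit does not differ when one lens is more often off-centre. Because the study is open-label, an unnamed variable also leaves room to choose it after the data have been seen.

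**Working it through.** **1. The plan's own figure.** Section 1.6.1 states "50 subjects are required to complete the study to provide 90% power, assuming a standard deviation of 1.5 units for intra-subject differences". The difference to be detected is 0.7 units. Alpha is not stated; I assume two-sided 5%.

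n = (1.5 × (1.960 + 1.282) / 0.7)² = 48.25, so 49. Paired t power at n = 50 is 89.9%. The stated 50 reproduces. It concerns handling on removal, and no power is claimed for lens fit.

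**2. Why the signed grade can be blind.** The documents give no grade distributions, so these are assumed. Take lens A at 5/90/5% and lens B at 20/60/20% over -1/0/+1, independent within subject.

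- Signed: P(B > A) = 0.05 × 0.80 + 0.90 × 0.20 = 0.22. By symmetry P(B < A) = 0.22, so there is nothing to detect.
- Absolute: P(|B| > |A|) = 0.90 × 0.40 = 0.36; P(|B| < |A|) = 0.10 × 0.60 = 0.06.

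**3. A test that suits the wording of 1.6 and is not blind.** The hypothesis is that the parameters are the same. Taken as equality of the two grade distributions in paired data, this is what the Stuart-Maxwell test examines (2 degrees of freedom for three grades). In the example the expected discordant counts between zero and non-zero are 50 × 0.36 = 18 and 50 × 0.06 = 3. The directional part is zero, so the statistic at expected counts is (18 − 3)² / (18 + 3) = 10.7. The 5% critical value is 5.99.

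**4. Simulated rejection rates** (50 pairs, one value per lens, two-sided 5%):

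| Grades at -1/0/+1 (%) | Signed rank, signed grade | Signed rank, absolute grade | Stuart-Maxwell |
|---|---|---|---|
| 5/90/5 vs 20/60/20 | 5% | 96% | 91% |
| 5/90/5 vs 15/70/15 | 5% | 71% | 59% |
| 10/80/10 vs 25/50/25 | 5% | 90% | 81% |
| 30/60/10 vs 10/60/30 (direction only) | 90% | 5% | 82% |

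I repeated these four rows; each agreed within about two percentage points.

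**5. When the worsening is not balanced.** The signed test recovers: 5/90/5 against 15/60/25 gives 17%, against 10/60/30 gives 55%, and against 5/60/35 gives 90%. The absolute grade gives 94–95% in all three.

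**6. What the obvious remedy would buy.** The remedy tests both the signed and the absolute grade, each at 2.5%. At least one rejects in 59–91% of the balanced cases and 84% of the directional case. Stuart-Maxwell gives 59–91% and 82%, so the pair offers little beyond one suitable test. For smaller balanced changes neither route does much: on the absolute grade alone, 5/90/5 against 10/80/10 gives about 27% and 10/80/10 against 15/70/15 gives 21%. The simulations use one value per lens, so they do not describe an analysis that averages two eyes.

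**The case for a change.** The best case for a change is that a signed-rank test on the recorded grade is the default many analysts would use, that naming the variable costs a line of text and no data, and that doing so beforehand removes a choice in an open-label study. The fit check at dispensing does not dispose of the point either, because the cancellation in the first three rows of the table happens wholly within -1 to +1.

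The arithmetic and the gap both stand. The step from gap to fault does not:

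- Section 1.6 names neither the signed grade nor a rank test. The power loss belongs to an analysis that the plan has not adopted.
- In every -1/0/+1 example, all eyes on both lenses meet the plan's own criterion for acceptable fit. Calling the wider spread worse fit is a definition brought from outside the plan.
- An absolute grade assumes that -1 and +1 are equally far from ideal. The grade descriptions are blacked out, so this cannot be checked. For movement, the two ends of the scale may be different faults that should not be merged.
- Nothing in the documents suggests a balanced two-sided difference. The lens table in the first amendment gives both lenses the same base curve (8.6 mm) and diameter (14.5 mm).

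**Conclusion.** No change to the plan follows. The visible text leaves the variable and the test for centration and movement unnamed. That is missing detail on a secondary outcome with no power target, and a sensible analyst can fill it before the analysis with a paired test that responds to both direction and spread. The worst case is real but conditional: about 5% rejection instead of 71–96% in the three balanced cases, and only if the analyst tests the signed grade alone. The alternative of prescribing the absolute grade exchanges one blind spot for another (5% against 90% for a purely directional shift) and rests on grade descriptions that cannot be seen. Section 1.6 already commits the final report to discussing departures from the statistical plan.

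These figures rest on assumed grade distributions, 50 pairs, independence within subject and two-sided 5%. With a within-subject correlation of 0.5, the three balanced cases still give 5% on the signed grade and 77–98% on the absolute grade. The primary outcome and the sample size are untouched.

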3.2.3 Dispensing 1 visit

Subjects should attend this visit wearing their spectacles. Subjects attending this visit wearing contact lenses should be rescheduled.

The following procedures will be performed (any ocular measurement procedures outlined below will be carried out on each eye):

1. [REDACTED]
[REDACTED]
2. Any medical or ocular issues since the last visit will be recorded.
3. [REDACTED]
4. The subject will apply the first randomised pair of lenses. Orientation of toric markings do not need to be taken into consideration.
5. Lenses are allowed to settle for five minutes.
6. Toric lens fit will be assessed as described in Section 3.2.2.
7. [REDACTED]
[REDACTED]
[REDACTED]
[REDACTED]
[REDACTED]
[REDACTED]
[REDACTED]
[REDACTED]
[REDACTED]
8. Lens fit will then be assessed using the following evaluations: horizontal and vertical centration, corneal coverage and movement, using the grading scales in
[REDACTED]
9. [REDACTED]
[REDACTED]
10. [REDACTED]
[REDACTED]
[REDACTED]
11. The investigator will confirm that lens fit [REDACTED] are satisfactory:
 - a. In the case of an unacceptable lens fit, proceed to the next randomised lens (on the same day, or as a separate visit).
 - b. In the case of unacceptable vision (less than 6/12), if in the opinion of the investigator an alternate lens from within the available power range would improve vision, then new lenses can be ordered and this visit repeated. If an alternate lens is not indicated then proceed to the next randomised lens (on the same day, or as a separate visit).
12. [REDACTED]
[REDACTED]

13. The subject will be issued with 10 pairs of contact lenses for the first study period.
14. The subject will then be discharged and asked to return for the one-week follow-up visit having worn the study lenses for at least two hours. Subjects should be asked to wear their lenses for a minimum of eight hours per day, five days per week.

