1.5 Study design

This will be a multi-centre, randomised, open-label, crossover, bilateral study, controlled by cross-comparison. Up to 55 subjects will use each lens type for a week in random sequence. Follow-up visits for each lens will be performed after one week of wear. Lenses will be worn on a daily wear, daily disposable wear schedule.

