3.2.5 Follow-up 2 visit

Subjects should attend wearing the study lenses which should have been in situ for at least two hours. Subjects who attend without lenses in situ for at least two hours will usually be rescheduled.

1. The same procedures as at Follow-up 1 (Section 3.2.4 above) will be carried out.
2. [REDACTED]
3. At the final visit (or when the subject is discontinued at an earlier visit) arrangements to issue the subject with their payment will be made, although they may have been asked by the investigator to attend a post-study follow-up visit. They should continue to use their lenses and solutions as advised, and seek aftercare for their contact lenses.

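### Do the secondary analyses of lens fit and biomicroscopy treat a subject's two eyes as independent?

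*Combined protocol and SAP*

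**What the plan says.** Section 1.5 describes a "multi-centre, randomised, open-label, crossover, bilateral study, controlled by cross-comparison", so both eyes wear the same lens type in each period. Sections 3.2.3 and 3.2.4 each state that "any ocular measurement procedures outlined below will be carried out on each eye". For the second follow-up, section 3.2.5 says "The same procedures as at Follow-up 1 (Section 3.2.4 above) will be carried out". At the initial visit (section 3.2.2) the staining instruction is also bilateral: "Instil sodium fluorescein (using a fluorescein ophthalmic strip wetted with saline) in both eyes".

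On outcomes, section 1.4 says "The primary outcome measure for this study is subjective handling on lens removal" and then "Secondary measures are lens fit parameters and biomicroscopy scores"; the text after that is redacted.

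On analysis, section 1.6 has a partly redacted sentence whose visible end says that certain outcomes will "be compared using linear regression models or other parametric methods". What those outcomes are is hidden. The lens fit sentence is visible in full: "Lens fit data are expected to be ordinal data and assessed with non-parametric approaches". No visible text gives the unit of analysis, a rule for combining or choosing eyes, or a subject or eye term.

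**The concern.** Each subject gives four values per sign: two eyes by two lenses. Ordinary regression and the standard rank tests assume independent units. If each eye's lens difference is entered as its own row, 50 subjects become 100 pairs. Where fellow eyes respond alike to a lens, the standard error is then too small, and the trial could report differences in fit or ocular physiology that 50 subjects do not support. Because the visible text does not name the unit, a reader cannot rule this out from section 1.6 alone.

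**Working it through.** **The plan's own figure.** Section 1.6.1 gives an SD of 1.5 for the within-subject difference, a meaningful difference of 0.7, 90% power and 50 completers. No alpha is stated; two-sided 5% is assumed.

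n = [1.5 × (1.960 + 1.282) / 0.7]² = 48.25, rounded up to 49. With the noncentral t, power is 89.9% at 50 and first passes 90% at 51. The stated 50 reproduces within rounding. It is a paired calculation with one difference per subject, so eye handling does not enter it.

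**Eye-level differences taken as independent.** Let ρ be the between-eye correlation of the lens difference. The documents do not give it, so a range is shown. For 50 subjects and 100 eyes:

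- variance inflation = 1 + ρ
- effective number of eyes = 100 / (1 + ρ)
- interval shortfall = 1 − 1/√(1 + ρ)
- actual type I error = 2 × [1 − Φ(1.96/√(1 + ρ))]

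| ρ (assumed) | Effective eyes | Interval too narrow by | Actual type I error |
|---|---|---|---|
| 0.1 | 91 | 5% | 6.2% |
| 0.3 | 77 | 12% | 8.6% |
| 0.5 | 67 | 18% | 11.0% |
| 0.7 | 59 | 23% | 13.3% |
| 0.9 | 53 | 27% | 15.5% |

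Simulation with 50 subjects agrees. For ρ from 0.3 to 0.9, the t-test on eyes rejects in 8.5% to 16.0% of null trials, and the signed-rank test on rounded grades in 7.3% to 15.7%.

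**One value per subject.** With the mean of the two eyes, the same simulations (ρ from 0 to 0.9) give 4.8% to 5.1% for the t-test and 4.4% to 5.4% for the signed-rank test.

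**Pairing ignored as well.** Suppose an ordinary regression took all 200 values as independent. Let a be the correlation of the same eye across lenses, b that of the two eyes with the same lens, and c that of opposite eyes across lenses. With σ² the variance of one value, the true variance of the lens difference is (1 + b − a − c)σ²/50. The naive variance is σ²/100 + σ²/100 = σ²/50. The ratio is 1 + b − a − c.

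- a = 0.5, b = 0.7, c = 0.4: ratio 0.8, actual type I error 2.8% (conservative).
- a = 0.2, b = 0.8, c = 0.15: ratio 1.45, actual type I error 10.4% (optimistic).

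In the first case the eye-paired correlation is ρ = (b − c)/(1 − a) = 0.3/0.5 = 0.6, and the eye-paired test would run at 12.1%. The same data can therefore give error on either side of 5%, depending on which naive analysis is imagined.

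**What the text commits to.** None of these naive analyses appears in the protocol. The parametric and non-parametric classes in section 1.6 both contain subject-level paired methods and clustered methods. Section 1.6.1 works with differences within subjects, and section 3.4 has the report give the number of subjects in each analysis. Neither settles the matter, but both lean towards the subject as the unit, and no visible text leans the other way.

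**The case for a change.** The strongest case for acting is that the lens fit sentence is complete and silent on eyes, so redaction cannot excuse it. The reporting rule in section 3.4 does not settle the unit either: a test on 100 pairs can still be reported as 50 subjects. The study is open-label and section 1.6 allows departures once the data distribution is seen, so right eye, left eye, mean or both could be chosen after the results are known. The remedy would cost one sentence.

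Some of this stands. The unit of analysis for lens fit is not stated, and stating it would be tidier. For biomicroscopy the same cannot be said, because the words that identify what the regression sentence covers are redacted.

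What does not stand is the step from silence to optimistic p-values. It reads the least suitable member into an open class of methods. It also needs a positive ρ, which the documents do not supply: this is the correlation of lens differences, from which stable subject effects common to both lenses cancel, so low values are possible. Nor is a blanket averaging rule free of cost. Section 3.2.2 describes centration and movement on a scale from −2 to +2, and grades of +1 and −1 in the two eyes would average to 0, hiding opposite departures. There is a case for leaving the choice to the analyst, outcome by outcome.

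**Conclusion.** No change is required. Both eyes are measured for each lens, and the visible plan does not say how they are combined for lens fit; for biomicroscopy this cannot be determined. That is a missing detail in secondary analyses, which a subject-level or clustered method fills within the existing wording.

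The inflation to about 6% to 16% holds only if eye-level lens differences are analysed as independent, with ρ between 0.1 and 0.9 and a two-sided 5% level, all of which are assumptions. A regression that also ignored the pairing could be conservative. The primary comparison, a score given by the subject, and the target of 50 completers are unaffected under any of these scenarios.
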